4. DATA HANDLING DEFINITIONS AND CONVENTIONS

4.1. Scheduled Study Evaluations and Study Periods

4.1.1. Day 1

Day 1 is the date that the participant is randomized.

4.1.2. Study Day

If a visit/reporting date is on or after Day 1, then the study day at the visit/reporting date will be calculated as

$$\text{Day \#} = (\text{visit/reporting date} - \text{Day 1 date} + 1).$$

If the visit/reporting date is before Day 1, then the study day at the visit/reporting date will be calculated as

$$\text{Day \#} = (\text{visit/reporting date} - \text{Day 1 date}).$$

A study day of -1 indicates 1 day before Day 1.

4.1.3. Baseline Value

Baseline is the last nonmissing measurement obtained before the first administration of INCAGN02385, INCAGN02390, or retifanlimab, unless otherwise defined.

When scheduled assessments and unscheduled assessments occur on the same day, and the time of the assessment or time of first dose is not available, use the following convention to determine baseline:

- If both a scheduled and an unscheduled assessment are available on the day of the first dose and the time is missing, use the scheduled assessment as baseline.
- If all scheduled assessments are missing on the day of the first dose and an unscheduled assessment is available, use the unscheduled assessment as baseline.

4.1.4. Handling of Missing and Incomplete Data

In general, values for missing data will not be imputed unless methods for handling missing data are specified in this section or relevant sections. The original reported dates collected on the eCRF should be used in all relevant listings. The following rules will be used for handling partial dates for analyses requiring dates.

When calculating time since diagnosis of cancer, partial cancer diagnosis date will be handled as follows:

- If only the day is missing, then the first day of the month will be used.
- If both the month and day are missing, then 01 JAN of the year will be used.
- If the diagnosis date is completely missing, then the time since diagnosis will not be calculated.

When the date of the last dose is used in deriving variables, such as duration of treatment or TEAE flag, a missing or partial date of the last dose will be handled as follows:

- If only the day is missing, then the earlier date of the last day of the month or the date that the participant discontinued treatment will be used.
- If both the month and day are missing, then the earlier date of 31 DEC of the year or the date that the participant discontinued treatment will be used.
- Otherwise, the date that the participant discontinued treatment will be used as the date of the last dose.

For relevant efficacy endpoints, partial date of death will be handled as follows in the calculation:

- If mmyyyy for the last known alive date = mmyyyy for the death date, then the death date will be set to the day after the last known alive date.
- If mmyyyy for the last known alive date < mmyyyy for the death date, then the death date will be set to the first day of the death month.
- Otherwise, the partial death date will not be imputed.

4.1.5. Cycle Length and Duration

Cycle 1 Day 1 is the day that the first dose of INCAGN02385, INCAGN02390, or retifanlimab is administered. The scheduled cycle length is 4 weeks. The actual Day 1 of subsequent cycles will correspond with the first day of administration of retifanlimab in that cycle.

4.2. Variable Definitions

4.2.1. Body Mass Index

Body mass index will be calculated as follows:

$$\text{BMI (kg/m}^2\text{)} = [\text{weight (kg)}] / [\text{height (m)}]^2.$$

4.2.2. Creatinine Clearance

Creatinine clearance by Cockcroft-Gault (1976) is estimated from serum creatinine (mg/dL) determination by using the following formula:

$$\text{Creatinine clearance (mL/min)} = [140 - \text{age (years)}] \times \text{weight (kg)} \times \{0.85^* \text{ for female participants}\} / [72 \times \text{serum creatinine (mg/dL)}].$$

*Note: For male participants use 1.0.

4.2.3. Prior and Concomitant Medication

Prior medication is defined as any nonstudy medication started before the randomization date.

Concomitant medication is defined as any nonstudy medication that is started:

- Before the randomization date and is ongoing throughout the study or ends on/after the date of first study medication administration, or
- On/after the randomization date and is ongoing or ends during the course of the study.

A prior medication could also be classified as "both prior and concomitant medication" if the end date is on or after the randomization date. In the listing, it will be indicated whether a medication is prior-only, concomitant-only, or both prior and concomitant.

For the purposes of analysis, all medications will be considered concomitant medications unless the medications can unequivocally be defined as not concomitant; that is, if the start date and end date are missing, then the medication is considered as concomitant medication.

5. STATISTICAL METHODOLOGY

5.1. General Methodology

Unless otherwise noted, SAS[®] software (SAS Institute Inc, Cary, NC; v9.4 or later) will be used for the generation of all tables, graphs, and statistical analyses. Descriptive summaries for continuous variables will include, but not be limited to the number of observations, mean, standard deviation, median, minimum, and maximum. Descriptive summaries for categorical variables will include the number and percentage of participants in each category.

No formal interim analyses for efficacy are planned for this study as noted in Section 9 of the Protocol; however, DSMB-related activities will be routinely conducted regarding the safety data.

5.2. Treatment Groups

This is a Phase 2, randomized, double-blind, controlled, parallel treatment group design study. Data will be summarized by treatment groups.

5.3. Analysis Populations

[Table 4](#) presents the populations for analysis.

Table 4: Populations for Analysis

Population	Description
ITT	
All participants who are randomized will constitute the ITT population. Treatment groups for this population will be defined according to the treatment assignment at the time of randomization regardless of the actual study drug the participant might take during their participation in the study.
 
The ITT population will be used for the summary of demographics, baseline characteristics, participant disposition, and analyses of all efficacy data.

Safety	
The safety population will include all participants who receive at least 1 dose of study treatment. Treatment groups for this population will be determined according to the actual treatment the participant received regardless of assigned treatment at the time of randomization.
 
The actual treatment received corresponds to:
 
The randomized treatment if the participant took at least 1 dose of that treatment.
 
The first treatment received if the randomized treatment was never received.
 
All safety analyses will be conducted using the safety population.

PK/pharmacodynamic evaluable	
The PK evaluable population will include all participants who received at least 1 dose of study treatment and provided at least 1 postdose serum sample (1 PK measurement). The study pharmacokineticist will review data listings of study drug administration and sample records to identify participants to be excluded from any analyses of PK data that may be performed.
 
The pharmacodynamic evaluable population will include all participants who received at least 1 dose of study treatment and provided at least 1 postdose plasma sample (1 pharmacodynamic measurement). The study research investigator will review data listings of pharmacodynamic data and sample records to identify participants to be excluded from analyses of pharmacodynamic data.

ADA evaluable	
The ADA evaluable population will include all participants who received at least 1 dose of study treatment and provided at least 1 ADA postdose sample. The ADA-related analysis may be conducted by the PK group.

Table 5 shows how the analysis populations are associated with the primary and secondary endpoints.

Table 5: Endpoints and Analysis Populations

Primary/Secondary Endpoint	Population	Hypothesis	Population-Level Summary Metric
PFS	ITT	
H1: TG3 is superior to TG1 with respect to PFS in all participants
 
H2: TG2 is superior to TG1 with respect to PFS in all participants
	Median PFS, HR
OS	ITT	NA	Median OS, HR
Objective response	ITT	NA	ORR difference
Disease control	ITT	NA	DCR difference
DOR	ITT ^a	NA	Median DOR
AEs	Safety	NA	Rate

Table 5: Endpoints and Analysis Populations (Continued)

Primary/Secondary Endpoint	Population	Hypothesis	Population-Level Summary Metric
AE impact on study treatment (treatment interruptions, dose reductions, and withdrawal of study treatment due to AEs)	Safety	NA	Rate

^a Responder subpopulation.

6. BASELINE, EXPOSURE, AND DISPOSITION

[Appendix A](#) provides a list of data displays. Sample data displays are included in a separate document.

6.1. Demographics, Baseline Characteristics, and Disease History

The ITT will be used for all baseline disease characteristics and demographic summaries and data listings. All variables will be summarized by treatment group with groups presented separately.

6.1.1. Demographics

The following demographics and baseline characteristics will be summarized by treatment group and listed for participants in the ITT population: age, sex, race, ethnicity, height, body weight, and BMI; creatinine clearance; and region of enrollment. Qualitative data will be summarized by contingency tables and quantitative data will be summarized by descriptive summary statistics.

6.1.2. Baseline Disease Characteristics and Disease History

Baseline disease characteristics and disease history will be summarized by treatment group and listed for participants in the ITT population including time since initial diagnosis, time since diagnosis of recurrent metastatic disease, smoking status (current or former, never), disease status (locally recurrent and metastatic, locally recurrent, or metastatic recurrence), site of primary tumor (hypopharynx, larynx, oral cavity or oropharynx), baseline ECOG performance status, and relevant biomarkers per the central laboratory analysis (eg, LAG-3 expression, PD-L1 expression, HPV p16 status). Other information collected in the eCRF may be listed in detail.

Time since diagnosis will be calculated as follows:

$$\text{Time since diagnosis (years)} = (\text{date of randomization} - \text{date of diagnosis} + 1) / 365.25.$$

6.1.3. Prior Therapy

The number of prior systemic cancer therapy regimens will be summarized by treatment group for all participants in the ITT population. The component drugs of prior systemic therapy regimens will be coded using the WHO Drug Dictionary. The number and percentage of participants who received each drug will be summarized by WHO drug class and WHO drug

preferred term. The regimen name, component drugs, start and stop dates, purpose of the regimen, best response, reason for discontinuation, and date of relapse/progression will be listed.

The number of participants who received prior radiation will be summarized for the ITT population. The prior radiotherapy body site, start and stop dates will be listed.

The number of participants who had prior surgery or surgical procedure for the malignancies under study will be summarized for the ITT population. The prior surgery date and description of the surgery/procedure will be listed.

6.1.4. Medical History

For participants in the ITT population, medical history will be summarized by assigned treatment group. This summation will include the number and percentage of participants with medical history for each body system/organ class as documented on the eCRF.

6.2. Disposition of Participants

The number and percentage of participants who were randomized, who were treated, who were ongoing with study treatment, who completed study treatment, who discontinued study treatment with a primary reason for discontinuation, who were still in the study, who completed the study, and who withdrew from the study with a primary reason for withdrawal will be summarized for the ITT population. The number of participants randomized by country and/or site will also be provided by treatment group. A death listing with date of death and cause of death will be provided.

6.3. Protocol Deviations

Important Protocol deviations will be summarized by category and listed.

6.4. Exposure

For participants in the safety population, a summary of exposure to each study drug (ie, INCAGN02385, INCAGN02390, and/or retifanlimab) or the treatment group will be summarized descriptively, if feasible, as the following:

- Total number of cycles of INCAGN02385, INCAGN02390, and retifanlimab
- Total number of infusions of INCAGN02385, INCAGN02390, and retifanlimab
- Total dose administered (mg): sum of the cumulative dose administered to each participant
 - If partial infusion is administered for a visit (ie, "No" was selected for the question "Was entire infusion administered?" in the Dosing eCRF), the actual dose administered at this visit will be calculated as (Estimated Volume Delivered [mL] / Prepared Volume [mL] × Dose Level of the Study Drug [mg])
- Average dose per infusion (mg): total dose administered (mg) / total number of infusions

- Duration of treatment with study drug (days): date of last dose of study drug – date of first dose of study drug + 1
- Dose intensity (mg/day): total dose administered (mg) / (duration of treatment + cycle length – 1)
- Relative dose intensity: actual dose intensity (mg/day) / planned dose intensity (mg/day)

Duration of exposure in months will be calculated based on the assumption that each month has 30.4375 days. The number and percentage of participants in each duration category (ie, 0 to 3 months, ≥ 3 months, ≥ 6 months, ≥ 9 months, ≥ 12 months, ≥ 18 months, ≥ 24 months, and other timepoints as applicable) will be summarized.

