Adherence to the study design requirements, including those specified in the SoA, is essential and required for study conduct.

Figure 1: Study Design Schema

[figure not shown]

Table 3: Schedule of Activities

Visit Day (Range)	Screening	Treatment						EOT	Safety Follow-Up	Survival Follow-Up	Notes
	Days –28 to –1	Cycle 1			Cycle 2+		Q8W (± 7 d)		EOT + 30 and 90 days (± 7 d)	Q12W (± 14 d)	
		Day 1	Day 8 (± 2 d)	Day 15 (± 2 d)	Day 1 (± 3 d)	Day 15 (± 2 d)					
Administrative procedures											
Informed consent	X										See Section 8.1.1 for details.
Contact IRT	X	X		X	X	X		X	X		See Section 8.1.3 for details.
Inclusion/exclusion criteria	X	X									See Section 5 for details.
Demographics and general and disease medical history	X										See Section 8.1.5 for details.
HPV p16 testing	X										Participants with primary oropharyngeal tumors must have known HPV status (determined locally; otherwise, request central testing per sponsor) prior to randomization. See Section 5.1 for details.
Prior/concomitant medications	X	X	X	X	X	X		X	X		Section 8.1.6 for details.
Administer retifanlimab		X			X						Retifanlimab administered on Day 1 of each cycle (Q4W). See Section 6.1 for details.
Administer INCAGN02385/placebo		X		X	X	X					Administered Q2W of each cycle. See Section 6.1 for details.
Administer INCAGN02390/placebo		X*		X	X	X					*Following completion of the Cycle 1 Day 1 INCAGN02390/placebo infusion, participants will be observed at the study site for 4 hours per Section 6.5.2.
Distribute reminder card		X	X	X	X	X		X	X		See Section 8.1.4 for details.
Safety assessments											
AE assessments	X	X	X	X	X	X		X	X		See Section 8.3.1 for details.
Physical examination/body weight/height	X	X	X	X	X	X		X	X		Complete physical exam at screening; targeted physical thereafter. Height at screening only. Body weight at screening and Day 1 of each cycle. See Section 8.3.2 for details.

Table 3: Schedule of Activities (Continued)

Visit Day (Range)	Screening	Treatment						EOT	Safety Follow-Up	Survival Follow-Up	Notes
	Days –28 to –1	Cycle 1			Cycle 2+		Q8W (± 7 d)		EOT + 30 and 90 days (± 7 d)	Q12W (± 14 d)	
		Day 1	Day 8 (± 2 d)	Day 15 (± 2 d)	Day 1 (± 3 d)	Day 15 (± 2 d)					
Safety assessments (continued)											

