7. DISCONTINUATION OF STUDY TREATMENT AND PARTICIPANT WITHDRAWAL

7.1. Discontinuation of Study Treatment

7.1.1. Reasons for Discontinuation

Participants **must** be discontinued from study treatment for the following reasons:

- Consent is withdrawn.

Note: Consent withdrawn means that the participant has explicitly indicated that they do not want to be followed any longer; in this case, no further data, except data in public domain, may be solicited from or collected on the participant. Participants may choose to discontinue study treatment and remain in the study to be followed for progression and survival.

- Confirmed or unequivocal PD per RECIST v1.1 as assessed by the investigator.

Note: Guidance for treatment with immunotherapy beyond initial objective disease progression is provided in Section 6.5.5.

- The participant is lost to follow-up as described in Section 7.3.
- Further participation would be injurious to the participant's health or well-being, in the investigator's medical judgment.
- Unacceptable toxicity as noted in Section 6.5.
- The participant has received the maximum duration of 2 years of study treatment.
- The investigator decides to discontinue the participant from study treatment.
- The study is terminated by the sponsor.
- The study is terminated by the local health authority, IRB, or IEC.

A participant **may** be discontinued from study treatment as follows:

- If, during the course of the study, a participant is found not to have met eligibility criteria, the medical monitor, in collaboration with the investigator, will determine whether the participant should be withdrawn from study treatment.
- If a participant is noncompliant with study procedures or study drug/treatment administration in the investigator's opinion, the sponsor should be consulted for instruction on handling the participant.

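### SAP 6.4 ends each drug's treatment duration at its last infusion and adds a 28-day cycle to every dose-intensity denominator, so fully dosed identical cycles show different exposure and dose intensity by drug

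*SAP*

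**What the plan says.** SAP 6.4 plans "a summary of exposure to each study drug (ie, INCAGN02385, INCAGN02390, and/or retifanlimab) or the treatment group", and SAP Appendix A lists a separate exposure table for each drug (Tables 3.1.1.1 to 3.1.1.3). The duration rule is "Duration of treatment with study drug (days): date of last dose of study drug – date of first dose of study drug + 1". Conversion to months is fixed: "Duration of exposure in months will be calculated based on the assumption that each month has 30.4375 days". The categories are "0 to 3 months, ≥ 3 months, ≥ 6 months, ≥ 9 months, ≥ 12 months, ≥ 18 months, ≥ 24 months", with other timepoints allowed as applicable.

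The same section defines "Dose intensity (mg/day): total dose administered (mg) / (duration of treatment + cycle length – 1" (closing bracket omitted here), and relative dose intensity as actual over planned dose intensity. SAP 4.1.5 states: "The scheduled cycle length is 4 weeks".

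Under Protocol 6.1, retifanlimab 500 mg is given on Day 1 of each cycle only. INCAGN02385 350 mg and INCAGN02390 400 mg, or their placebos, are given on Days 1 and 15. The visit windows are ±3 days for Day 1 and ±2 days for Day 15. Protocol 7.1.1 lists as a mandatory reason to stop: "The participant has received the maximum duration of 2 years of study treatment".

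**The concern.** The interval that the last infusion covers is left out of the duration. That interval is 28 days for retifanlimab and 14 days for the Q2W antibodies, so the omission is unequal across drugs given over the same cycles. Protocol 6.5.1 requires all study drugs to be interrupted together, and all three to stop together for toxicity. For full cycles, a between-drug difference in the exposure tables therefore comes from the formula and not from treatment.

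The section is also inconsistent with itself. The dose-intensity denominator does extend past the last dose, but by a whole cycle for every drug, although two of the three are dosed every half cycle.

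At stake is how the exposure and compliance tables read. Fully compliant participants would appear under-dosed on the two antibodies under test, and a participant who completed the 2-year course would usually be tabulated below 24 months.

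**Working it through.** The documents give no exposure figure to reproduce; this is date arithmetic from the stated rules.

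**Inputs.** Cycle of 28 days (SAP 4.1.5); 30.4375 days per month and the duration and dose-intensity formulas (SAP 6.4); doses, dosing days and windows (Protocol 6.1); 2-year maximum (Protocol 7.1.1).

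**Duration as written.** The last dose in cycle c falls on day 28(c−1)+1 for retifanlimab and day 28(c−1)+15 for the Q2W drugs. With the first dose on day 1, that day number is the SAP duration.

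| Full cycles | Retifanlimab | Q2W drugs | Cut-off between them |
|---|---|---|---|
| 4 | 85 d = 2.79 mo | 99 d = 3.25 mo | 3 mo (91.3 d) |
| 7 | 169 d = 5.55 mo | 183 d = 6.01 mo | 6 mo (182.6 d) |
| 14 | 365 d = 11.99 mo | 379 d = 12.45 mo | 12 mo (365.25 d) |
| 26 | 701 d = 23.03 mo | 715 d = 23.49 mo | none; both below 24 mo |

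The 4-cycle split survives the visit windows: retifanlimab 3 days late is 88 days = 2.89 months, and a Q2W dose 3 + 2 days early is day 94 = 3.09 months. The other two splits are narrow. At 7 cycles, a Q2W dose one day early (day 182) falls below 182.6. At 14 cycles, a retifanlimab dose one day late (day 366) passes 365.25.

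**The 24-month row.** The threshold is 24 × 30.4375 = 730.5 days, so a counted duration of 731 days is needed. Cycle 27 Day 1 falls on nominal day 729, giving 729/30.4375 = 23.95 months. Moved 2 days within the ±3-day window, it gives 731/30.4375 = 24.02 months. Separately, 26 × 28 = 728 days is below 730.5 before any question of where counting stops.

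**Relative dose intensity as written, 4 full cycles, cycle length 28.**
- Retifanlimab: 4 × 500 / (85 + 27) = 17.86 mg/day; planned 500/28 = 17.86; ratio 100%.
- INCAGN02385: 8 × 350 / (99 + 27) = 22.2 mg/day; planned 350/14 = 25; ratio 88.9%.
- INCAGN02390: 8 × 400 / 126 = 25.4 mg/day; planned 400/14 = 28.6; ratio 88.9%.

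In general, n on-schedule Q2W infusions give a denominator of 14(n−1) + 1 + 27 = 14(n+1) days and hence a ratio of n/(n+1). This rises towards 100% but never reaches it: 52 infusions (26 cycles) give 52/53 = 98.1%.

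**With the dosing interval added** (last − first + 28 or + 14), all three drugs have 112 days = 3.68 months at 4 cycles, 196 days = 6.44 at 7, and 392 days = 12.88 at 14, so the splits disappear. INCAGN02385 dose intensity becomes 2800/112 = 25 mg/day = 100%. At 26 cycles all three have 728 days = 23.92 months, still below 24; that row needs its own change.

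**The case against.** First-to-last dose is an explicit, reproducible definition of treatment duration, and choosing it is not in itself an error. Any rule for covered time is a convention: with the 18.4-day retifanlimab half-life in Protocol 2.1.5, exposure does not end at day 28 either. SAP 6.4 also reports cycles, infusions and total dose, and SAP 6.2 counts participants who completed treatment, so four cycles will show as four cycles for every drug. Placebos follow the same schedule, so the convention favours no treatment group. All of this stands, and it keeps the point small. It does not remove the between-drug artefacts, because the categories and the dose-intensity ratio are tabulated by drug.

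A reader might infer more than the documents support:

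- **That the 24-month row cannot be reached.** The Protocol caps time and not cycles, and a last dose at about day 731 reaches the row at the 2-year limit. The last-infusion rule is not the sole cause either, since 728 days is already short of 730.5. On the planned timeline, with the final analysis about 20 months after enrolment starts (Protocol 10.1, SAP 3.2), nobody could have 24 months of treatment under any formula. The row matters only at a later data cut-off.
- **That every participant loses 27 days (retifanlimab) or 13 days (Q2W drugs).** Those who die, or are still on treatment at data cut-off, within the last dosing interval lose fewer.
- **That adverse event results are affected.** SAP 8.2 plans numbers and percentages of participants in the safety population, with a fixed 90-day window after the last dose; no exposure-adjusted rate uses this duration.

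**Conclusion.** The point holds as a minor but real defect in descriptive reporting. Fully dosed identical cycles fall in different exposure categories by drug at 4, 7 and 14 cycles, robustly to the visit windows only at 4. Fully compliant Q2W dosing cannot show 100% relative dose intensity: 88.9% after 4 cycles, 98.1% after 26. The top duration row is practically empty on the nominal schedule, partly because it is set in months while treatment runs in 28-day cycles. No efficacy result, power, alpha or AE percentage changes.

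This rests on three readings that the SAP does not spell out: duration of exposure in months is the same variable as duration of treatment in days; cycle length in the dose-intensity formula means the 28 days of SAP 4.1.5 for all drugs; and planned dose intensity is dose over dosing interval. If cycle length was meant as each drug's own interval, the dose-intensity part disappears (2800/(99 + 13) = 25 mg/day), but the SAP should then say so. The duration part does not depend on that.

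**What to change.** In SAP 6.4:

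1. Define duration per drug as last dose − first dose + that drug's dosing interval (28 days for retifanlimab; 14 days for INCAGN02385 and INCAGN02390, including placebo). For the exposure-duration table only, truncate at death or data cut-off.
2. Use the untruncated version as the dose-intensity denominator in place of duration + cycle length − 1. Truncation must not carry over, because death soon after an on-schedule infusion would push relative dose intensity above 100%.
3. Replace the top category by at least 104 weeks (728 days) or 26 cycles completed. Counting completed cycles is less sensitive to visits a day or two early.

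The cost is one derivation and one row label. Reported durations become slightly longer. Where the last visit was a Day 1, retifanlimab will exceed the Q2W drugs by 14 days (stopping at cycle 4 Day 1: 112 against 98 days). That difference is genuine, because the Day 15 dose was not given.

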6. STUDY TREATMENT

6.1. Study Treatments Administered

Table 8 presents the study treatment information.

Table 8: Study Treatment Information

	Study Treatment 1	Study Treatment 2	Study Treatment 3
Study treatment name:	Retifanlimab (INCMGA00012)	INCAGN02385/placebo	INCAGN02390/placebo
Dose formulation:	Solution for infusion	Solution for infusion	Solution for infusion
Unit dose strength(s)/ dose level(s):	25 mg/mL in a glass vial for single use Dose level: 500 mg Q4W	50 mg/mL Dose level: 350 mg Q2W	50 mg/mL Dose level: 400 mg Q2W
Route of administration	IV (30-minute infusion with filter followed by 10-minute flush)	IV (30-minute infusion with filter followed by 10-minute flush)	IV (30-minute infusion with filter followed by 10-minute flush)
Packaging and labeling	Study drug will be provided in a vial. Each vial will be labeled as required per country requirement.	Study drug will be provided in a vial. Each vial will be labeled as required per country requirement.	Study drug will be provided in a vial. Each vial will be labeled as required per country requirement.
Status of treatment in participating countries:	Investigational	Investigational	Investigational

The order of administration of study drugs on Day 1 of each cycle should be retifanlimab, followed by INCAGN02385/placebo, followed by INCAGN02390/placebo.

The order of administration of study drugs on Day 15 of each cycle should be INCAGN02385/placebo followed by INCAGN02390/placebo; retifanlimab is not administered on Day 15.

As outlined in Table 8, infusions are 30 minutes each with a 10-minute flush followed by the next infusion. For additional details regarding infusion of study drugs, refer to the Pharmacy Manual.

Study treatment will be administered for up to 2 years, or until discontinuation criteria are met (see Section 7.1.1). Study treatment may be administered \pm 3 days of the scheduled Day 1 for each cycle (except for Cycle 1 Day 1, on which the study treatment will be administered specifically on Day 1) and \pm 2 days of the scheduled Day 15 for each cycle. INCAGN02385/placebo and INCAGN02390/placebo doses should not be administered < 12 days apart.

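### The SAP's dose-intensity formula adds a 28-day cycle for all three drugs, so a participant given every two-weekly dose on time over whole cycles is reported below 100%

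*SAP*

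**What the plan says.** SAP 6.4 (Exposure) calls for "a summary of exposure to each study drug (ie, INCAGN02385, INCAGN02390, and/or retifanlimab"), so each drug is summarised separately. Three of its definitions matter here:

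- Duration: "Duration of treatment with study drug (days): date of last dose of study drug", minus the date of the first dose, plus 1.
- Dose intensity: "Dose intensity (mg/day): total dose administered (mg) / (duration of treatment + cycle length" minus 1).
- Relative dose intensity: "Relative dose intensity: actual dose intensity (mg/day) / planned dose intensity (mg/day"). The planned value is not defined.

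SAP 4.1.5 gives a single cycle length for the trial: "The scheduled cycle length is 4 weeks". There is no drug-specific value.

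Protocol Table 8 (Section 6.1) gives two different dosing intervals: retifanlimab "Dose level: 500 mg Q4W", INCAGN02385 "Dose level: 350 mg Q2W" and INCAGN02390 "Dose level: 400 mg Q2W".

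SAP Appendix A plans one exposure table per drug (Tables 3.1.1.1 to 3.1.1.3), all marked for the DSMB package. Protocol 10.4.4 also lists dose intensity among the exposure measures.

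**The concern.** Duration, as defined, stops on the day of the last dose. The term added to it should therefore stand for the period that the last dose covers. One 28-day term for all drugs does this for retifanlimab but not for drugs given every 14 days.

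Protocol 6.5.1 does not allow dose changes, and it allows a Day 15 administration to be left out after a toxicity delay. Relative dose intensity in this trial is therefore mainly a measure of delays, omissions and partial infusions. A value of n/(n+1) is what one missed dose out of n+1 would look like, so a fully dosed participant is shown with one missed dose that did not happen. A reader of the per-drug tables could conclude that the two added antibodies were delivered less well than retifanlimab in the same people.

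**Working it through.** The documents print no dose-intensity figure, so there is none to reproduce. The check applies the SAP 6.4 formula to full doses given exactly on schedule.

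**Inputs**
- Cycle length 28 days (SAP 4.1.5).
- Retifanlimab 500 mg every 28 days, INCAGN02385 350 mg every 14 days, INCAGN02390 400 mg every 14 days (Protocol Table 8).
- Assumption: planned intensity is scheduled dose over dosing interval. This gives 500/28 = 17.86, 350/14 = 25.0 and 400/14 = 28.57 mg/day. Counting per cycle gives the same values for the two-weekly drugs: 700/28 = 25.0 and 800/28 = 28.57.

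**General form.** With n doses at interval t, duration = t(n − 1) + 1, and the denominator = t(n − 1) + 1 + 28 − 1 = t(n − 1) + 28.

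**Retifanlimab (t = 28).** The denominator is 28n. Intensity = 500n/28n = 17.86 mg/day, and the relative value is 100% for every n. The formula is right for this drug.

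**Two-weekly drugs (t = 14).** The denominator is 14(n − 1) + 28 = 14(n + 1). The relative value is n/(n + 1).

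For whole completed cycles (even n, last dose on Day 15):

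| Doses | Days in those cycles | SAP denominator | INCAGN02385 mg/day (planned 25.0) | INCAGN02390 mg/day (planned 28.57) | Relative |
|---|---|---|---|---|---|
| 2 | 28 | 42 | 700/42 = 16.67 | 800/42 = 19.05 | 66.7% |
| 4 | 56 | 70 | 1400/70 = 20.00 | 1600/70 = 22.86 | 80.0% |
| 6 | 84 | 98 | 2100/98 = 21.43 | 2400/98 = 24.49 | 85.7% |
| 12 | 168 | 182 | 4200/182 = 23.08 | 4800/182 = 26.37 | 92.3% |
| 52 | 728 | 742 | 18200/742 = 24.53 | 20800/742 = 28.03 | 98.1% |

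Each row divides by 14 days more than the cycles lasted. The shortfall is largest for short exposure and never disappears.

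**With the dosing interval in place of cycle length.** The denominator is 14(n − 1) + 14 = 14n. Intensity is 25.0 and 28.57 mg/day, and the relative value is 100% for every n. Retifanlimab is unchanged.

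**The case against.** *A per-cycle denominator may be intended.* This stands for odd n. When the last dose falls on Day 1 of a cycle, 14(n + 1) is a whole number of cycles, and the formula counts the Day 15 dose of the started cycle as not given. One dose is then 1 of 2 (50%), and seven doses are 7 of 8 (87.5%). Those figures follow a defensible convention and should not be called errors. The argument fails for even n: a per-cycle denominator would be 14n, and the SAP formula still runs 14 days past the end of the last completed cycle.

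*Planned intensity is undefined, so the percentages are conditional.* True. Relative intensity would read 100% if the planned value were computed over the same lengthened denominator, but the SAP does not say so. The absolute mg/day would still be too low.

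*The summaries are only descriptive.* Also true. They enter no hypothesis, and the number of infusions, total dose and average dose per infusion are reported alongside and are unaffected. The table shells are in a separate document, so it cannot be confirmed that relative intensity appears in the tables marked for the DSMB.

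*A stronger reading.* Because the shortfall shrinks with longer exposure, a reader might infer that arms with longer PFS would look better dosed. The documents do not support this. TG1 receives placebo for both two-weekly drugs, and nothing says that placebo is scored in mg. Active INCAGN02390 is given only in TG3. Active INCAGN02385 is given in TG2 and TG3, which share the same planning hazard ratio of 0.6 against TG1.

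**Conclusion.** The formula is wrong as written for INCAGN02385 and INCAGN02390, and no other section corrects it. For participants who completed whole cycles with every dose full and on time, it understates relative dose intensity under either convention: by 33 percentage points after one cycle (100 − 66.7), 14 after three (100 − 85.7) and 8 after six (100 − 92.3). Retifanlimab in the same participant reads 100%.

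The percentages rest on two assumptions: planned intensity is the scheduled dose over its interval, and doses fall exactly on schedule. Doses given early or late within the visit windows would shift them. The absolute understatement (21.4 against 25.0 mg/day for INCAGN02385 after three cycles) needs only the second assumption.

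The effect is confined to the exposure summaries for the two drugs (Tables 3.1.1.1 and 3.1.1.2). PFS, power and alpha are untouched. The comparison that is distorted is between drugs within a participant, not between arms.

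**What to change.** In SAP 6.4, replace cycle length in the dose-intensity formula with the scheduled dosing interval of the drug being summarised, as given in Protocol Table 8: 28 days for retifanlimab and 14 days for INCAGN02385 and INCAGN02390. Add one sentence defining planned dose intensity as the scheduled dose divided by that same interval.

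This changes the calculation only, not the dosing schedule. The cost is one phrase, one added definition and a drug-specific constant in the exposure program.

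There is one downside. A participant who stops after a Day 1 dose without receiving the Day 15 dose would read 100%. That is the convention the formula already applies to retifanlimab, where doses not given after the last one do not count, and a table footnote can say so.
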